**Table J16 Inhibitors of CYP2C19 or CYP3A4 that AstraZeneca Recommends not to be Combined with Selumetinib**

CYP2C19	CYP3A4
	Dronedarone
	Crizotinib
	Fedratinib
	Letermovir
	Aprepitant
	Lefamulin
	Imatinib
	Verapamil
	Netupitant
	Nilotinib
	Tofisopam
	Berotralstat
	Ciprofloxacin
	Voxelotor
	Isavuconazole
	Cimetidine

a There is literature evidence for esomeprazole causing weak CYP2C19 inhibition at 20 mg QD and moderate CYP2C19 inhibition at 80 mg QD, between this (eg, 20 mg bid) it is not confirmed at what dose esomeprazole changes from a weak to moderate inhibitor, therefore dose levels > 20 mg QD should be avoided with selumetinib.

b There is literature evidence for cannabidiol causing moderate CYP2C19 inhibition at doses of 750 mg bid for 7 days. There are no data at what dose cannabidiol becomes a moderate inhibitor, or if lower doses of cannabidiol cause CYP2C19 inhibition.

bid, twice daily; CYP, cytochrome P450; QD, once daily.

**Table J17 Inducers of CYP3A4 that AstraZeneca Recommends not to be Combined with Selumetinib**

CYP3A4 Strong	CYP3A4 Moderate
Rifampin	Efavirenz
Mitotane	Dabrafenib
Rifapentine	Cenobamate
Apalutamide	Bosentan
Phenytoin	Rifabutin
Carbamazepine	Lorlatinib
Enzalutamide	Nafcillin
Ivosidenib	Phenobarbital
St John's wort	Modafinil
Lumacaftor	Pexidartinib
	Etravirine
	Elagolix
	Sotorasib
	Telotristat ethyl
	Nevirapine

CYP, cytochrome P450.

**J 2 Restricted, Prohibited, and Permitted Concomitant Medications/Therapies**

Restricted and prohibited concomitant medications/therapies are described in [Table J18](#). Refer also to the dose modification guidelines for management of study intervention-related toxicities in Section [6.6](#).

**Table J18 Restricted and Prohibited Medications/Therapies**

Prohibited medication/class of drug	Usage (including limits for duration permitted and special situations in which it is allowed)
Other IMP	Not allowed for 4 weeks or 5 half-lives (whichever is longer) prior to the first dose of study intervention.  Not allowed during the study.
MEK inhibitor	Prior exposure is prohibited.  Not allowed during the study (with the exception of selumetinib study intervention).

**Table J18      Restricted and Prohibited Medications/Therapies**

Prohibited medication/class of drug	Usage (including limits for duration permitted and special situations in which it is allowed)
Other systemic PN target treatment (including chemotherapy, immunotherapy, targeted therapy, biologic therapy, or monoclonal antibodies)	Not allowed for 4 weeks or 5 half-lives (whichever is longer) prior to the first dose of study intervention.  Not allowed during the study.
Radiotherapy	Not allowed for 6 weeks prior to the start of study intervention.  Radiotherapy (before or during the study) not allowed on target or non-target PNs.
Growth factors	Not allowed within the 7 days prior to screening assessment.
Blood transfusion (red blood cells or other blood products)	Not allowed within the 28 days prior to screening assessment.
Multivitamins containing vitamin E	Must be stopped 7 days prior to initiation of study intervention.  Not allowed during the study.
Herbal supplements or medications known to be strong or moderate inhibitors or inducers of CYP3A4 or strong or moderate inhibitors of CYP2C19. Substrates of OAT3.	Must be safely discontinued at least 14 days or 5 half-lives (whichever is longer) before the first dose of study intervention.  Strong or moderate inducers of CYP3A4 are not allowed at any time during the study. During the first cycle, concomitant use of strong or moderate inhibitors of CYP3A4 or CYP2C19 should be avoided until after the PK assessment. During the remainder of the study, if concomitant use of selumetinib with strong or moderate CYP3A4 or CYP2C19 inhibitors is not avoidable, then the selumetinib dose should be reduced as shown in Table J15 . The dose of selumetinib should be reduced for the duration of concomitant therapy with the strong or moderate CYP3A4 or CYP2C19 inhibitor and for 5 half-lives afterwards. After the washout of the inhibitor is complete, the selumetinib dose can be re-escalated. The participant should be monitored closely for potential toxicities.  Selumetinib may affect the plasma/serum concentrations of substrates of OAT3 and they should be given with caution.

CYP, cytochrome p450; IMP, investigational medicinal product; MEK = mitogen activated protein kinase; OAT3, organic anion transporter 3; PN, plexiform neurofibroma.

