3 Participants must have completed a pain diary (PAINS-pNF) with a documented chronic target PN pain score for at least 4 days out of 7 days for at least 2 weeks during the screening period. Participants must have stable chronic PN pain medication use at baseline, defined as no clinically significant changes to prescribed chronic PN pain medication within 28 days prior to study enrolment or planned at the time of study enrolment.

4 Eastern Cooperative Oncology Group performance status of 0 or 1 with no deterioration over the previous 2 weeks prior to baseline or day of first dosing. Participants who are wheelchair bound because of paralysis secondary to a PN should be considered ambulatory when they are in their wheelchair. Similarly, participants with limited mobility secondary to a need for mechanical support (such as an airway PN requiring tracheostomy or continuous positive airway pressure) will also be considered ambulatory for the purpose of the study.

5 Participants must have at least one measurable PN, defined as a PN of at least 3 cm measured in one dimension, which can be seen on at least 3 imaging slices and have a reasonably well-defined contour. Participants who have undergone surgery for resection of a PN are eligible provided the PN was incompletely resected and is measurable. The target PN will be defined as the clinically most relevant PN, which is measurable by volumetric MRI analysis.

6 Adequate organ and marrow function as follows with no blood transfusions (of red blood cells/other blood products) within 28 days prior to screening assessment and no growth factors within 7 days prior to screening assessment:

- Haemoglobin  $\geq 9.0$  g/dL.
- Absolute neutrophil count  $\geq 1.5 \times 10^9/L$ .

- Platelet count  $\geq 100 \times 10^9/\text{L}$ .
- Total bilirubin  $\leq 1.5 \times \text{ULN}$  or  $\leq 3 \times \text{ULN}$  in the presence of documented Gilbert's syndrome (unconjugated hyperbilirubinemia).
- Alanine aminotransferase and AST  $\leq 2.5 \times \text{ULN}$ .
- Calculated creatinine clearance  $\geq 60 \text{ mL/min}$  as determined by Cockcroft-Gault (using actual body weight).

Males:

$$\text{CrCL} = \frac{\text{Weight (kg)} \times (140 - \text{Age})}{72 \times \text{serum creatinine (mg/dL)}}$$

Females:

$$\text{CrCL} = \frac{\text{Weight (kg)} \times (140 - \text{Age})}{72 \times \text{serum creatinine (mg/dL)}} \times 0.85$$

7 All participants must be able to swallow whole capsules.

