### **Prior/Concomitant Therapy**

- 13 Prior exposure to MEK inhibitors.
- 14 Receipt of the last dose of systemic PN target treatment (including chemotherapy, immunotherapy, targeted therapy, biologic therapy, or monoclonal antibodies) within 4 weeks prior to the first dose of study intervention or 5 half-lives of the respective systemic PN target treatment, whichever is longer.
- 15 Has received radiotherapy in the 6 weeks prior to the start of study intervention or any prior radiotherapy directed at the target or non-target PN.
- 16 Major surgical procedure (excluding placement of vascular access) or significant traumatic injury within 4 weeks of the first dose of study intervention or an anticipated need for major surgery during the study.
- 17 Receiving herbal supplements or medications at doses known to be strong or moderate inducers of CYP3A4 unless such products can be safely discontinued at least 14 days or 5 half-lives (whichever is longer) before the first dose of study intervention (see [Appendix J](#)).
- 18 With the exception of chronic PN pain medication, receiving herbal supplements or medications at doses known to be strong or moderate inhibitors of the CYP2C19 and CYP3A4 enzymes, unless such products can be safely discontinued at least 14 days or 5 half-lives (whichever is longer) before the first dose of study intervention (see [Appendix J](#)).
- 19 Any multivitamin containing vitamin E must be stopped at least 7 days prior to initiation of study intervention.

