## 6.5 Concomitant Therapy

Any concomitant treatment, procedure, or other medication considered necessary by the investigator for the participant's safety and wellbeing, or vaccine (including over-the-counter or prescription medicines, vitamins, and/or herbal supplements) that the participant is receiving from the time of screening or receives during the study including the 30 day follow-up period following the last dose of study intervention must be recorded in the eCRF along with:

- Reason for use.
- Dates of administration including start and end dates.
- Dosage information including dose and frequency.

The AstraZeneca Medical Monitor should be contacted if there are any questions regarding concomitant or prior therapy.

If any concomitant therapy is administered due to new or unresolved AE, it should be recorded.

Participants must be instructed not to take any medications, including over-the-counter products, without first consulting with the investigator.

Strong or moderate **inducers** of **CYP3A4** are not allowed at any time during the study. During the first cycle, concomitant use of strong or moderate **inhibitors of CYP3A4 or CYP2C19**, with the exception of chronic PN medication, should be avoided until after the PK assessment. If concomitant use of selumetinib with strong or moderate CYP3A4 or CYP2C19 inhibitors is not avoidable, then the selumetinib dose should be reduced as shown in [Appendix J Table J15](#). For chronic PN pain medication fulfilling the above criteria, selumetinib should be initiated at a reduced dose as shown in [Appendix J Table J15](#). The dose of selumetinib should be reduced for the duration of concomitant therapy with the strong or moderate CYP3A4 or CYP2C19 inhibitors and for 5 half-lives afterwards. After the washout of the inhibitor is complete, the selumetinib dose can be re-escalated. The participant should be monitored closely for potential toxicities.

In vitro, selumetinib is an inhibitor of OAT3. The potential for a clinically relevant effect on the PK of concomitantly administered substrates of OAT3 cannot be excluded and they should be administered with caution.

Selumetinib capsules contain vitamin E in the form of D- $\alpha$ -tocopheryl polyethylene glycol

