## Appendix J Concomitant Medications

### J 1 Guidance Regarding Potential Interactions with Concomitant Medications

Throughout the study, participants should avoid changes to, or the addition of, all concomitant medications and, in particular, any that may affect the metabolism of selumetinib (eg, CYP2C19 or CYP3A4 moderate/strong inhibitors, as well as CYP3A4 moderate/strong inducers), unless considered clinically indicated. The use of any natural/herbal products or other “folk remedies” should be discouraged, but use of these products, as well as use of all vitamins, nutritional supplements, and all other concomitant medications must be recorded in the eCRF.

Strong or moderate **inducers** of CYP3A4 are not allowed at any time during the study. During the first cycle concomitant use of **strong or moderate inhibitors of CYP3A4 or CYP2C19**, with the exception of chronic PN pain medication, should be avoided until after the PK assessment. During the remainder of the study, if concomitant use of selumetinib with strong or moderate CYP3A4 or CYP2C19 inhibitors is not avoidable, then the selumetinib dose should be reduced as shown in [Table J15](#). For chronic PN pain medication fulfilling the above criteria, selumetinib should be initiated at a reduced dose as shown in [Table J15](#). The dose of selumetinib should be reduced for the duration of concomitant therapy with the strong or moderate CYP3A4 or CYP2C19 inhibitor and for 5 half-lives afterwards. After the washout of the inhibitor is complete, the selumetinib dose can be re-escalated. The participant should be monitored closely for potential toxicities.

In vitro, selumetinib is an inhibitor of OAT3. The potential for a clinically relevant effect on the PK of concomitantly administered substrates of OAT3 (eg, methotrexate, furosemide benzylpenicillin, baricitinib and tenofovir) cannot be excluded and they should be administered with caution.

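### Table J18 requires CYP3A4/CYP2C19 inhibitors to be stopped before dosing without the chronic PN pain medication exemption given in exclusion 18, Section 6.5 and Appendix J 1, and it contradicts itself on OAT3 substrates

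*Protocol*

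**What the plan says.** Exclusion 18 in protocol Section 5.2 opens with a carve-out: "With the exception of chronic PN pain medication, receiving herbal supplements or medications at doses known to be strong or moderate inhibitors" of CYP2C19 and CYP3A4 is exclusionary, "unless such products can be safely discontinued at least 14 days or 5 half-lives (whichever is longer) before the first dose of study intervention". It refers the site to Appendix J.

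Section 6.5 and Appendix J 1 tell sites to avoid these inhibitors in the first cycle until the PK assessment has been done, and both exempt the participant's chronic PN drug. Both then deal with the participant who starts treatment while still taking it: "For chronic PN pain medication fulfilling the above criteria, selumetinib should be initiated at a reduced dose".

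Table J18 in Appendix J 2 has one row for inhibitors and inducers of CYP3A4, "strong or moderate inhibitors of CYP2C19. Substrates of OAT3". The instruction for that row begins "Must be safely discontinued at least 14 days or 5 half-lives (whichever is longer) before the first dose of study intervention". It goes on: "During the first cycle, concomitant use of strong or moderate inhibitors of CYP3A4 or CYP2C19 should be avoided until after the PK assessment". Neither sentence mentions chronic PN pain medication. The cell ends by saying that OAT3 substrates should be given with caution. That agrees with Section 6.5, where the potential effect on "substrates of OAT3 cannot be excluded and they should be administered with caution".

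Inclusion 3 in Section 5.1 requires stable chronic PN pain medication. It rules out clinically significant changes to the prescribed drug in the 28 days before enrolment or "planned at the time of study enrolment".

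**The concern.** A site that follows exclusion 18 and a site that follows Table J18 would handle the same participant differently. The first leaves the analgesic in place and starts study treatment. The second stops the analgesic before the first dose, and by doing so may put the participant outside inclusion 3. Section 5 and Section 8 allow no waivers, so a site cannot settle the conflict by exception.

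For OAT3 substrates the question is whether the drug is stopped before dosing at all. Appendix J 1 gives furosemide and methotrexate as examples, so this is an instruction about drugs that a participant may need. The protocol should answer it in one way.

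**Working it through.** No figure in the plan is involved and no arithmetic bears on the contradiction. The check sets the passages side by side.

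| Place in protocol | Stop inhibitors before first dose | Avoid inhibitors in first cycle | OAT3 substrates |
|---|---|---|---|
| Exclusion 18 (Section 5.2) | Yes; chronic PN pain medication exempt | Not addressed | Not mentioned |
| Section 6.5 | Not addressed | Yes; chronic PN medication exempt | Give with caution |
| Appendix J 1 | Not addressed | Yes; chronic PN pain medication exempt | Give with caution |
| Table J18 (Appendix J 2) | Yes; no exemption | Yes; no exemption | In the row to be stopped; same cell says give with caution |

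1. **Same drugs, same washout.** Exclusion 18 and Table J18 cover the same inhibitor classes and use the same interval, 14 days or 5 half-lives, whichever is longer. The only difference is the exemption.

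2. **Table J18 is cited, not stray.** Exclusion 18 refers to Appendix J. The lifestyle restrictions in Section 5.2 send the site to Appendix J 2. Section 6.5 describes J 2 as the more detailed account. The table's usage column is headed as listing the special situations in which a drug is allowed, and this situation is absent.

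3. **Where the conflict lies.** After the first cycle, Table J18 allows inhibitor use that cannot be avoided, as the other sections do. The disagreement is confined to the pre-dose stop and the first cycle.

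4. **Collision with inclusion 3.** Enrolment means consent (Section 9.2, note to the sample size table), and screening lasts up to 28 days. If consent is given on Day -28, the latest stop that satisfies Table J18 is Day -14, which is 28 - 14 = 14 days after consent. A stop intended from the outset is then a change planned at enrolment. A stop made in the 28 days before consent falls in the other window that inclusion 3 closes. What escapes is a stop more than 28 days before consent, a change that is not clinically significant, a product that is not prescribed, or a need to stop that was not foreseen at consent. Compliance with Table J18 therefore could breach inclusion 3, but need not.

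5. **The starting rule.** If Table J18 and inclusion 3 are both applied as written, few if any participants remain for the Section 6.5 and Appendix J 1 provision on starting selumetinib alongside such a drug.

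6. **OAT3 substrates.** No exclusion criterion names them. Three statements (Section 6.5, Appendix J 1 and the end of the Table J18 cell) say caution. The opening instruction of the same cell, read against the row label, says stop. This second contradiction lies within Table J18 and against Section 6.5 and J 1; exclusion 18 is not involved.

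**The case against.** The best case against is that this is a small drafting slip. Entry is governed by the numbered criteria, and exclusion 18 states the exemption plainly. Appendix J 1 repeats it before the reader reaches Table J18, and Section 6.5 directs questions to the sponsor's medical monitor. The group concerned may be nearly empty: none of the pain drugs named as examples in SAP Table 2 (acetaminophen, pregabalin, gabapentin, amitriptyline, duloxetine, codeine, morphine) appears in Table J16. Cannabidiol does, but its footnote reports moderate inhibition at 750 mg twice daily and no data on lower doses, and the documents do not say that it is used for PN pain. On OAT3, three consistent statements outweigh the layout of one row.

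Much of this stands. Table J18 is a medication table, so its effect is that the participant may not be dosed while on the drug, not that a numbered criterion fails. The group may well be small, although Appendix J 1 says the Table J16 list is not exhaustive. What does not stand is the suggestion that a careful site would always reach the same answer, because Section 6.5 itself calls J 2 the more detailed source.

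A reader might go further and infer that stopping an analgesic during screening raises the baseline pain score and so distorts the PAINS-pNF key secondary comparison. The documents do not support that. If inclusion 3 keeps these participants out, they contribute no baseline. If some enter, the stop comes before a 1:1 blinded randomisation stratified on baseline pain, so both arms are exposed to it alike, and the MMRM adjusts for baseline score and baseline-by-cycle (SAP Section 4.2.2.1.5). No figure is given for how far pain would rise or in how many participants.

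**Conclusion.** The contradiction is established from the text alone. Exclusion 18, Section 6.5 and Appendix J 1 provide for participants who stay on a chronic PN pain drug that inhibits CYP3A4 or CYP2C19; Table J18 does not. It also gives two instructions for OAT3 substrates in one cell. This is a conflicting rule on eligibility in practice and on stopping drugs, not a missing detail.

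Its reach cannot be sized. The documents do not give the number of participants taking such a drug, and no between-arm bias is shown. The inclusion 3 limb assumes that the drug is prescribed and that stopping it counts as a clinically significant change.

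A reader might also infer from Table J18 that OAT3 substrates are prohibited. The caution wording in the same cell, in Section 6.5 and in Appendix J 1 does not allow that conclusion. It allows only the conclusion that the protocol is inconsistent.

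**What to change.** Reconcile exclusion 18, inclusion 3, Section 6.5, Appendix J 1 and Table J18 so that two things are each stated once and consistently:

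- the status, before the first dose and in the first cycle, of chronic PN pain medication that is a strong or moderate CYP3A4 or CYP2C19 inhibitor, and how that fits with inclusion 3;
- the status of OAT3 substrates before and during treatment.

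Section 6.5 should use the same term for the exempt drug throughout; its first-cycle sentence omits the word pain. Which rule applies to either class is for the sponsor's clinical team to decide.

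The cost is a protocol wording change, chiefly in one table, and a clarification letter to sites. No new data and no change to the statistical analysis are needed.

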## **Appendix K Changes Related to Mitigation of Study Disruptions Due to Cases of Civil Crisis, Natural Disaster, or Public Health Crisis**

Note: Changes below should be implemented only during study disruptions due to any of or a combination of civil crisis, natural disaster, or public health crisis (eg, during quarantines and resulting site closures, regional travel restrictions and considerations if site personnel or study participants become infected with SARS-CoV-2 or similar pandemic infection) during which participants may not wish to or may be unable to visit the study site for study visits. These changes should only be implemented if allowable by local/regional guidelines and following notification from AstraZeneca and instructions on how to perform these procedures will be provided at the time of implementation.

Please note that during civil crisis, natural disaster, or public health crisis, some study assessments and procedures may not be conducted due to international or local policies or guidelines, hospital or clinic restrictions and other measures implemented to ensure the participant's safety. If in doubt, please contact the AstraZeneca Medical Monitor.

### **Reconsent of Study Participants During Study Interruptions**

During study interruptions, it may not be possible for the participants to complete study visits and assessments on site and alternative means for carrying out the visits and assessments may be necessary, eg, remote visits. Reconsent should be obtained for the alternative means of carrying out visits and assessments and should be obtained prior to performing the procedures described in Section 8. Local and regional regulations and/or guidelines regarding reconsent of study participants should be checked and followed. Reconsent may be verbal if allowed by local and regional guidelines (note, in the case of verbal reconsent the ICF should be signed at the participant's next contact with the study site). Visiting the study sites for the sole purpose of obtaining reconsent should be avoided.

### **Rescreening of Participants to Reconfirm Study Eligibility**

Additional rescreening for screen failure due to study disruption can be performed in previously screened participants. The investigator should confirm this with the designated AstraZeneca Medical Monitor.

In addition, during study disruption there may be a delay between confirming eligibility of a participant and either enrolment into the study or commencing of dosing with study intervention. If this delay is outside the screening window specified in Section 5.3 the participant will need to be rescreened to reconfirm eligibility before commencing study procedures. This will provide another opportunity to re-screen a participant. The procedures detailed in Table 1 must be undertaken to confirm eligibility using the same randomisation number as for the participant.

